17.2.1. Observational Population

The Observational population includes all subjects rolled over from the EN3835-201 study who do not receive any treatment in the current study. The safety analyses for subjects who received no EN3835 treatment in the current study will be performed using this population.

17.2.2. Safety Population

The Safety population will include all subjects who receive at least 1 dose of EN3835 in the current study. All safety analyses will be performed using this population.

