8.3.1.4. Endo-Sponsored Phase 2b Study EN3835-201

EN3835-201 was a double-blind, placebo-controlled study of 350 adult women randomized to EN3835 0.84 mg or placebo in a 1:1 ratio. Each subject received up to 3 treatment sessions of study drug separated by approximately 21 days; last visit was Day 71. Efficacy was evaluated using a Clinician-Reported Photonumeric Cellulite Severity Scale (CR-PCSS), a Patient-Reported Photonumeric Cellulite Severity Scale (PR-PCSS), the Hexsel Cellulite Severity Scale (CSS), Investigator Global Aesthetic Improvement Scale (I-GAIS), Subject Global Aesthetic Improvement Scale (S-GAIS), and a subject satisfaction assessment. Subjects that completed study EN3835-201 were offered the option of participating in study EN3835-202.

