9. OBJECTIVES

9.1. Primary Objective

The primary objective of this study is to assess long-term safety of EN3835 0.84 mg at scheduled intervals over 1 year (12 months) or more in all subjects with EFP who elect to enroll in this open-label trial regardless of their decision to receive treatment (re-treatment or re-dosing) of open-label EN3835 or opt to receive no treatment.

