17. STATISTICAL CONSIDERATIONS AND METHODS

17.1. Determination of Sample Size

Approximately 350 subjects that completed the EN3835-201 study will enroll in the current study. This sample size should be adequate to determine long term safety and cellulite assessments of EN3835.

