17.2. Subject Cohorts and Subject Populations

Subjects will be classified into 1 of 4 different cohorts depending on where they receive the treatment of EN3835 in relation to where they received treatment in study EN3835-201. The 4 cohorts are:

1. Observational subjects only - subjects who received EN3835 in study EN3835-201 but do not receive any injections in the current study.
2. Re-treatment subjects - subjects who received EN3835 in study EN3835-201 and receive EN3835 in the current study in the same quadrant that was treated in the EN3835-201 study. This will only be allowed for subjects who have baseline severity ratings in the current study at or worse than the baseline seen in study EN3835-201 for both the CR-PCSS and PR-PCSS of the quadrant.
3. Re-dosing subjects - subjects who received EN3835 in study EN3835-201 and receive EN3835 in the current study in a quadrant different than the EN3835-treated quadrant in study EN3835-201.
4. Initial treatment subjects - subjects who received placebo in study EN3835-201 and receive EN3835 in the current study.

All efficacy and safety analyses will be done within the classified cohort. Durability of treatment effects is defined as the time from onset of change from baseline of PR-PCSS and CR-PCSS in the quadrant treated in study EN3835-201 [REDACTED], where possible, in which the treated quadrant returns to baseline cellulite severity ratings of PR-PCSS and CR-PCSS in an EN3835-treated quadrant. Durability will be determined for all subjects that were treated with EN3835 in either EN3835-202 or EN3835-201. If sequential visit [REDACTED] are not available for that quadrant due to retreatment or [REDACTED], then the singular time point at which ratings return to baseline will be the durability cessation date.

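### Sections 17.2, 17.2.1 and 17.2.2 conflict on which subjects the safety analyses use, and no pooled ever-exposed set is defined for the primary safety objective

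*Combined protocol and SAP*

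**What the plan says.** The primary objective (9.1) is long-term safety of EN3835 0.84 mg in all subjects "who elect to enroll in this open-label trial regardless of their decision to receive treatment". Three parts of section 17.2 then say which subjects the safety analyses use.

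- 17.2.2: "The Safety population will include all subjects who receive at least 1 dose of EN3835 in the current study. All safety analyses will be performed" on that set. The synopsis gives the same definition.
- 17.2.1: "The Observational population includes all subjects rolled over from the EN3835-201 study who do not receive any treatment in the current study". The section assigns to this set the safety analyses of subjects untreated in the current study.
- 17.2: safety and efficacy are analysed within four cohorts. Cohort 1 is "subjects who received EN3835 in study EN3835-201 but do not receive any injections in the current study". Cohorts 2 and 3 were dosed in both studies. Cohort 4 received placebo in EN3835-201 and EN3835 in EN3835-202.

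On size, 17.1 states: "Approximately 350 subjects that completed the EN3835-201 study will enroll in the current study". It adds: "This sample size should be adequate to determine long term safety and cellulite assessments of EN3835". Section 8.3.1.4 describes the parent trial as a "study of 350 adult women randomized to EN3835 0.84 mg or placebo in a 1:1 ratio".

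**The concern.** Each of the three sections gives a different answer to who is in the denominator of a long-term EN3835 safety rate. Under 17.2.2, a woman treated in EN3835-201 who declines open-label treatment contributes to no safety analysis. Under 17.2.1 she does contribute, but alongside women who never received the drug. Under 17.2 she is kept apart from them, and the never-exposed women have no place.

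Never-exposed subjects can arise by two routes. Section 10.1 lets any enrolled subject choose no treatment, and 12.1.4 keeps a subject with no qualifying quadrant under observation without treatment.

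If 17.2.1 is programmed as written, the rate among observed-only subjects mixes exposed and unexposed women and will usually understate a drug-related event. If 17.2.2 is programmed as written, late events in women exposed only in EN3835-201 drop out. Neither gives one overall rate among everyone who received EN3835.

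**Working it through.** **Plan's own figure.** The current 17.1 gives no event rate, precision or formula, so its figure of about 350 cannot be re-derived. It equals the full number randomized in EN3835-201.

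**Set membership.** The definitions, applied to the four possible histories:

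| Parent arm | Dosed in 202 | Safety (17.2.2) | Observational (17.2.1) | Cohort (17.2) | Ever exposed |
|---|---|---|---|---|---|
| EN3835 | yes | in | out | 2 or 3 | yes |
| EN3835 | no | out | in | 1 | yes |
| Placebo | yes | in | out | 4 | yes |
| Placebo | no | out | in | none | no |

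Safety and Observational do not overlap, and together they hold every enrolled subject. Cohorts 1 to 4 together are exactly the ever-exposed subjects. No named analysis population matches the last column.

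**Inputs for size.**
- Subjects per parent arm: 350/2 = 175, from 8.3.1.4, assuming all randomized subjects roll over.
- fA and fP are the shares of the active and placebo parent arms dosed in EN3835-202. The documents give neither. fA = 50% and fP from 50% to 100% are assumed.

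**Formulas.**
- Safety = 175(fA + fP)
- Ever exposed = 175(1 + fP)
- Exposed but outside Safety = 175(1 − fA)
- Observational = 175(1 − fA) + 175(1 − fP)
- Never-exposed share of Observational, s = (1 − fP) / [(1 − fA) + (1 − fP)]
- Pooled Observational rate = (1 − s) × 5% + s × b, where b is the rate in never-exposed subjects

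**Results at fA = 50%** (exposed outside Safety = 87.5 in every row):

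| fP | Safety | Ever exposed | Share of exposed outside Safety | Observational | s | Rate, b = 0% | Rate, b = 2% |
|---|---|---|---|---|---|---|---|
| 50% | 175 | 262.5 | 33% | 175 | 50% | 2.5% | 3.5% |
| 75% | 218.75 | 306.25 | 29% | 131.25 | 33% | 3.3% | 4.0% |
| 90% | 245 | 332.5 | 26% | 105 | 17% | 4.2% | 4.5% |
| 100% | 262.5 | 350 | 25% | 87.5 | 0% | 5.0% | 5.0% |

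Example for the second row: s = 43.75/131.25 = 33.3%, and 66.7% × 5% = 3.3%. The 5% and 2% rates are illustrations. Active-arm uptake matters too: at fP = 75%, s is 25% with fA = 25% and 50% with fA = 75%.

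**Precision.** The one-sided 95% upper bound with zero events is 1 − 0.05^(1/n). It is 0.85% at n = 350 and 1.70% at n = 175. At fA = 50% and fP = 90% it is 1.22% for the Safety population (n = 245) and 0.90% for an ever-exposed set (n = 332.5).

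**The case against.** The strongest reply is the cohort rule in 17.2. Safety is to be analysed within cohort, cohort 1 admits only women given EN3835 in EN3835-201, and the four cohorts together are the exposed subjects. A reader might infer from 17.2.1 and 17.2.2 that the primary safety rates simply have wrong denominators. The documents do not support that, because exposed-only denominators can be assembled from the cohorts. Nor is anyone lost: the objective names all enrolled subjects, and Safety plus Observational cover them. Former placebo subjects could go straight to Screening B after unblinding (12.1.3), so few may have stayed untreated. All analyses are descriptive, and no test depends on these sets.

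These points stand, but they do not settle which rule governs. Nothing says the cohorts are to be pooled. Section 17.6 summarizes adverse events by a treatment group that is not defined for this open-label study, and 17.6.4 tabulates treatment-emergent events without mentioning cohorts. Section 12.1.4 also calls a placebo subject's second open-label course re-treatment or re-dosing, whereas 17.2 reserves those cohorts for women dosed in EN3835-201. No separate SAP text in the file resolves this.

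Two other strong readings fail. One is that, for women dosed in both studies, the months between courses are discarded. No section says so: the abbreviations list counts treatment-emergent events from the first injection of study drug without naming the study, and Table 2 times observation visits from Day 1 of EN3835-201. The origin is unstated rather than wrong. The other is that the exposed sample is only 175. That is roughly the number exposed at entry, and placebo subjects who elect treatment add to it.

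**Conclusion.** The concern holds as a conflict between three sections and a missing definition. The Safety population omits subjects exposed only in EN3835-201 yet is given every safety analysis. The Observational population mixes those subjects with the never-exposed. The cohort rule separates them but leaves untreated placebo subjects without a cohort. No pooled ever-exposed set serves the primary objective. The Safety population is still a proper denominator for events after dosing in EN3835-202.

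The size is conditional. With 175 per parent arm and 50% active-arm uptake, 25% to 33% of exposed subjects fall outside the Safety population over placebo-arm uptake of 100% down to 50%. The never-exposed share of the Observational population runs from 0% to 50% over the same range. The matching fall of a 5% event to as low as 2.5% needs a zero rate in the never-exposed. With a 2% background rate the lowest reading in the table is 3.5%, and with full placebo uptake there is no dilution.

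**What to change.** 1. Add an ever-exposed safety set to 17.2: at least one EN3835 injection in EN3835-201 or EN3835-202, with time zero at the first EN3835 injection. State whether adverse events recorded in EN3835-201 are carried in.
2. Keep subjects dosed in EN3835-202 as a named subset, and reword 17.2.2 so that it no longer claims every safety analysis.
3. Report the Observational population (17.2.1) separately by parent arm, without pooling the two.
4. Add a never-exposed cohort to 17.2 for former placebo subjects who remain untreated.
5. In 17.1, state that about 175 subjects enter already exposed if all 350 roll over, plus placebo subjects who elect treatment, so that 350 is not read as the exposed number.

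Subject-year rates would be a useful addition but are optional.

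The cost is wording and programming, using parent-study data the sponsor holds. No visit or procedure is added. A Safety definition covering either study stood in the plan before Amendment 3, so the idea is not new to it. The ever-exposed set is never smaller than the current Safety population, although it falls below 350 unless every placebo subject is treated.

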17.2.3. Effectiveness Population

The Effectiveness population includes all safety subjects who have a baseline and at least 1 post-baseline assessment on both the CR-PCSS and PR-PCSS on the quadrant selected for treatment in the current study. All analysis of effectiveness will be based on this population.

17.2.4. Durability Populations

Overall Durability Population: This population is defined as all active responders who have both CR-PCSS and PR-PCSS at 180 days or above. The active responders are subjects treated with EN3835 with improvements of at least 1 level on each scale (CR-PCSS and PR-PCSS) from the baseline.

17.2.4.1. Durability Population for Double-blind Treated Subjects

This population is defined as all subjects in the durability population who showed an improvement of at least 1 level on each scale (CR-PCSS and PR-PCSS) from the baseline for the quadrant treated with EN3835 in double-blind study EN3835-201.

17.2.4.2. Durability Population for Open-label Treated Subjects

This population is defined as all subjects in the durability population who showed an improvement of at least 1 level on both the CR-PCSS and the PR-PCSS from the baseline for the quadrant treated with EN3835 in the open-label study (current EN3835-202 study), and did not have the same quadrant treated in EN3835-201.

17.3. Subject Disposition

The number of subjects included in each study population will be summarized. The number and percentage of subjects completed and discontinued will be presented. Reasons for discontinuation as recorded on the eCRF will be summarized (number and percentage) for all subjects.

17.4. Demographics and Other Baseline Characteristics

Demographic and baseline characteristics, including age, race, and baseline values will be summarized for the Observational population, the Safety population, the Effectiveness population, and the Durability population using descriptive statistics. The descriptive statistics will include the number and percentage for categorical response variables and number, mean, standard deviation, minimum, and maximum for continuous variables.

17.5. Efficacy Analyses

Cellulite assessments (efficacy) include:

- PR-PCSS: 5-point scale ranging from 0 (no cellulite) to 4 (severe cellulite) (screening visit [Baseline], Days 22, 43, and 71). Also will be done at Day 90, Day 180, Day 270, and Day 360/end of study visits for observational assessments.

- CR-PCSS: 5-point scale ranging from 0 (no cellulite) to 4 (severe cellulite) (screening [Baseline], Days 22, 43, and 71). Also will be done at Day 90, Day 180, Day 270, and Day 360/end of study visits for observational assessments.
- Investigator rating of cellulite severity using the total scores from the Hexsel CSS scale: scores can range from 0 to 15 (screening [Baseline] and Day 71). Also will be done at Day 360/end of study visits for observational assessments.
- I-GAIS: 7-point scale ranging from 3 (very much improved) to -3 (very much worse) (Day 71). Also will be done at Day 360/end of study visit for observational assessments.
- S-GAIS: 7-point scale ranging from 3 (very much improved) to -3 (very much worse) (Day 71). Also will be done at Day 360/end of study visit for observational assessments.
- Subject satisfaction with cellulite treatment assessment: 5-point scale ranging from +2 (very much satisfied) to -2 (very much dissatisfied) (Day 71). Also will be done at Day 360/end of study visit for observational assessments.

All cellulite assessments will be done by treated quadrant. For initial treatment subjects who have 2 quadrants treated, each quadrant will be evaluated separately.

17.5.1. Efficacy Analysis

The composite endpoints for cellulite severity are the proportions of composite responders defined as subjects with an improvement in severity from baseline of at least 2 (or 1) levels of severity in the CR-PCSS and an improvement in severity from baseline of at least 2 (or 1) levels of severity in the PR-PCSS.

These endpoints, will be summarized by treated quadrant and overall (buttocks and thighs) and by study day using appropriate descriptive statistics.

Other endpoints for treated quadrants include:

- Proportion at each level of improvement in the PR-PCSS:
 - Proportion of patient responders defined as subjects with an improvement in severity from baseline of at least 2 levels of severity in the PR-PCSS
 - Proportion of patient responders defined as subjects with an improvement in severity from baseline of at least 1 level of severity in the PR-PCSS
- Proportion at each level of improvement in the CR-PCSS:
 - Proportion of Investigator responders defined as subjects with an improvement in severity from baseline of at least 2 levels of severity in the CR-PCSS (Investigator rated)
 - Proportion of Investigator responders defined as subjects with an improvement in severity from baseline of at least 1 level of severity in the CR-PCSS (Investigator rated)

- Proportion of responders at each level of the I-GAIS:
 - Proportion of Investigator global responders defined as subjects with a response of 1 (improved) or better in the Investigator GAIS assessment
- Proportion of responders at each level of the S-GAIS:
 - Proportion of subject global responders defined as subjects with a response of 1 (improved) or better in the subject GAIS assessment
- Proportion of responders at each level of the subject satisfaction with cellulite treatment
- Change in the Hexsel CSS total score from screening visit

All endpoints will be summarized by treated region (buttock or thigh) and overall and by study day using appropriate descriptive statistics.

Observational endpoints include:

- Proportions of composite responders defined as subjects with an improvement in severity from baseline of at least 2 (or 1) levels of severity in the CR-PCSS and an improvement in severity from baseline of at least 2 (or 1) levels of severity in the PR-PCSS.
- Proportion at each level of improvement in the PR-PCSS:
 - Proportion of patient responders defined as subjects with an improvement in severity from baseline of at least 2 levels of severity in the PR-PCSS
 - Proportion of patient responders defined as subjects with an improvement in severity from baseline of at least 1 level of severity in the PR-PCSS
- Proportion at each level of improvement in the CR-PCSS:
 - Proportion of Investigator responders defined as subjects with an improvement in severity from baseline of at least 2 levels of severity in the CR-PCSS (Investigator rated)
 - Proportion of Investigator responders defined as subjects with an improvement in severity from baseline of at least 1 level of severity in the CR-PCSS (Investigator rated)
- Hexsel CSS total score changed from the study EN3835-201 baseline at Day 71 of study EN3835-201 and Day 360/end of study of the current study (EN3835-202).

These endpoints will be summarized by treated region (buttock or thigh) and overall and by study day using appropriate descriptive statistics.

17.5.2. Durability of Treatment Effect

Durability of treatment effects will be presented as the number and percentage of treatment failure (or recurrence) among those active responders by follow-up time period, ie, 180 days, 360 days, 540 days, and 720 days. The treatment failure (recurrence) is defined as active

responders whose CR-PCSS and PR-PCSS return to the baseline in an EN3835-treated quadrant during a certain follow-up period.

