EN3835-201 if subject was treated with EN3835. Each treatment session will consist of up to 12 injections (0.07 mg/0.3 mL per injection) of EN3835 for a dose of 0.84 mg and volume of 3.6 mL. Only a quadrant with moderate (rating of 3) or severe (rating 4) level of severity as assessed by the subject and investigator using the PR-PCSS and the CR-PCSS, respectively, will be eligible for treatment; if more than 1 eligible quadrant exists, the quadrant selected will be at the discretion of the subject. Treatments will be administered on Days 1, 22, and 43; subjects will be assessed for safety on Days 1, 22, 43, and 71 and for cellulite severity assessments at Screening visit and on Days 22, 43, and 71. After Day 71, they will be observed every 3 months in each treated quadrant (including both open-label and double-blind treated quadrants, if different quadrants were treated across both studies). Durability of open-label treatment with EN3835 will be assessed for up to 1 year (Day 360). Durability beyond Day 360 will be assessed in subjects who received active treatment in EN3835-201 and showed a composite improvement of at least 1 level on both the CR-PCSS and the PR-PCSS. In these subjects, the original quadrant treated in EN3835-201 will be assessed until the end of the current study, in addition to any treated quadrants occurring in the current study. Assessments of durability beyond Day 360 may also include subjects who opted not to receive additional treatments in EN3835-202.
Number of subjects (planned): Approximately 350
Study center(s): 15 sites in the United States
Diagnosis and inclusion/exclusion criteria:
Qualification for the Open-label Observation Phase of the Study
Inclusion criteria for observation:

 1. Voluntarily sign and date an informed consent agreement 2. Have participated in and completed the double-blind study EN3835-201 3. Be willing to apply sunscreen to any treated quadrant before each exposure to the sun while participating in the study (ie, screening through end of study)
Exclusion criteria for observation:
None
Qualification for the Open-label Treatment Phase of the Study
Inclusion criteria for treatment:

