10. INVESTIGATIONAL PLAN

10.1. Study Design

This open-label extension study will be performed at multiple centers currently participating in the double-blind, placebo-controlled, parent trial (EN3835-201) in the United States. The open-label extension study will enroll up to 350 subjects. Subjects who completed the entire double-blind study and sign an informed consent will be eligible to enter this open-label extension.

After the Sponsor has broken the EN3835-201 study drug blind, subjects enrolled in the open-label study will have the following options:

- To have no EN3835 treatments in study EN3835-202
- If received EN3835 in study EN3835-201, may elect to have a qualifying quadrant other than the one treated in study EN3835-201 treated with EN3835 (termed *re-dosing*)
- If received EN3835 in study EN3835-201 and the cellulite severity scores of the treated quadrant have returned to or are greater than EN3835-201 baseline scores, may elect to have the previously treated quadrant retreated with EN3835 (termed *re-treatment*)
- If received placebo in study EN3835-201, may elect to have a qualifying quadrant treated with EN3835; also may elect to have a second qualifying quadrant treated with EN3835 after completing the treatment course

Subjects enrolled in study EN3835-202 who elect to receive EN3835 treatment (either re-treatment, re-dosing, or a first treatment) must meet specific inclusion and exclusion criteria for eligibility during re-screening (Screening B) prior to EN3835 dosing.

Following completion of safety and cellulite assessments at Day 71 of the double-blind study (EN3835-201), subjects will be asked if they wish to continue in the open-label extension to the double-blind study (Screening A). At the time of entry into the open-label study, subjects and Investigators will remain blinded to study drug. Until the EN3835-201 study drug blind is broken by the Sponsor, subjects will undergo observation-only visits at 3-month intervals \pm 7 days (relative to the initial dose in the double-blind study) where both safety and cellulite severity assessments of the treated quadrant will be made.

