11.3.2. Exclusion Criteria for Observation

1. Retreatment of the same quadrant in EN3835-202 and EN3835-201.
2. Has used any of the following for the treatment of EFP on the thighs or buttocks since treatment in EN3835-201, or intends to use any of the following at any time during the course of the study:
 - Liposuction on the side of the body selected for treatment during the EN3835-201 study
 - Injections (eg, mesotherapy); radiofrequency device treatments; laser treatment; or surgery (including subcision and/or powered subcision) within the selected treatment quadrant
 - Endermologie or similar treatments within the selected treatment quadrant
 - Massage therapy within the selected treatment quadrant
 - Creams (eg, CelluveraTM, TriLastin[®]) to prevent or mitigate EFP within the selected treatment quadrant

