12.1.3.1. Three-Month Assessments

Subjects will return within 20 days (± 4 days) of completion of the double-blind study for the first of 4 safety and cellulite severity evaluation visits. Assessments to be completed at these visits are detailed in Table 2. Subjects are to return at 3-month intervals until they have completed at least 12 months from Day 1 of the double-blind study. At these visits, the quadrant previously treated with EN3835 in the EN3835-201 study or quadrants treated with EN3835 in the

open-label study will be evaluated. If the quadrant treated in study EN3835-201 is retreated in the open-label study, the 3-month assessments will reset to treatment visit 1/Day 1 of the open-label treatment and the study visits will continue as described in [Table 3](#) followed by 3-month assessments as described in [Table 2](#). If a different quadrant is treated in the open-label study, the 3-month assessments of both the quadrant treated in the double-blind study (EN3835-201) and the quadrant treated in the open-label study will continue.

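### Durability is reported as crude recurrence percentages with no stated denominator or censoring rule, so the 180- to 720-day figures can be biased in either direction

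*Combined protocol and SAP*

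**What the plan says.** All references are to Protocol Amendment 4.

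- **Measure.** Section 17.5.2 gives the "number and percentage of treatment failure (or recurrence) among those active responders by follow-up time period". The periods are 180, 360, 540 and 720 days, and the text does not say whether they are cumulative. A failure is a responder "whose CR-PCSS and PR-PCSS return to the baseline in an EN3835-treated quadrant".
- **Definition.** Section 17.2 defines durability as a time, from onset of change until the quadrant is back at baseline on both scales. Part of that sentence is redacted. If re-treatment prevents sequential visits, the single visit showing return to baseline dates the end of durability.
- **Population.** Section 17.2.4 admits "all active responders who have both CR-PCSS and PR-PCSS at 180 days or above". Sections 17.2.4.1 and 17.2.4.2 define double-blind and open-label subsets. Section 17.2, by contrast, says durability will be determined for everyone treated with EN3835 in either study.
- **Re-treatment.** Under section 10.1, a quadrant treated with EN3835 in EN3835-201 may be re-treated if "the cellulite severity scores of the treated quadrant have returned to or are greater than EN3835-201 baseline scores". After that, "the 3-month assessments will reset to treatment visit 1/Day 1 of the open-label treatment" (section 12.1.3.1). "Retreatment of the same quadrant in EN3835-202 and EN3835-201" also bars observation beyond Day 360 (section 11.3.2).
- **Follow-up.** The synopsis limits open-label durability to Day 360. Tables 2 and 4 schedule ratings every 90 days from Day 90 to Day 720, and early-termination ratings share the Day 360 and Day 720 columns.

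**The concern.** The quantity of interest is a time to an event, and follow-up ends at different times for different quadrants. A percentage at a fixed day then depends on who is in the denominator and on how incomplete follow-up is handled. Section 17.5.2 settles neither.

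Three features make the choice matter. Entry depends on being rated at or after Day 180, so a responder who recurs and leaves before then is lost. Follow-up of an original course can be ended by re-treatment, which is open only to quadrants that have already failed. Open-label quadrants cannot supply data at 540 or 720 days, yet the text does not confine those periods to EN3835-201 quadrants.

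Durability over 12 months and beyond 12 months are two of the secondary objectives in section 9.2, and extending durability follow-up was one of the main reasons for Amendment 4. As written, the choice that decides these figures could be made after the data are seen.

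**Working it through.** The plan states no recurrence rate, precision or formula for durability, so there is no figure to reproduce. Every rate below is an assumption.

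**Assumptions.** Recurrence probability h = 8% (or 3%) at each 90-day visit. Recurrence is permanent. Loss to follow-up is unrelated to recurrence unless stated.

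**True cumulative recurrence.** F = 1 − (1 − h)^k after k visits. For h = 0.08:
- Day 180 (k = 2): 1 − 0.92² = 15.4%
- Day 360 (k = 4): 1 − 0.92⁴ = 28.4%
- Day 720 (k = 8): 1 − 0.92⁸ = 48.7%

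**Day 180 condition.** Let q be the share of Day 90 recurrences that never enter the population. The reported value is (F − hq)/(1 − hq).
- q = 0.3: (0.1536 − 0.024)/0.976 = 13.3%
- q = 0.7: (0.1536 − 0.056)/0.944 = 10.3%
- q = 0: no bias

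Early loss that is unrelated to recurrence leaves the Day 180 value unchanged.

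**Denominator at Day 720.** Three readings fit the text:
- A: everyone in the durability population, with all observed failures carried forward.
- B: only quadrants still rated at that day, with re-treated ones gone.
- C: quadrants of known status, with failures carried forward and non-failures who left dropped.

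Simulating 400,000 responders per scenario gives the results below (%). *Loss* means 5% dropout per visit plus 30% not continuing past Day 360. In these runs a quadrant that recurs at Day 90 and is re-treated does not enter the population.

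| h | Re-treated | Loss | True | A | B | C | Kaplan-Meier, all responders |
|---|---|---|---|---|---|---|---|
| 8% | 0 | no | 48.6 | 48.6 | 48.6 | 48.6 | 48.6 |
| 8% | 70% | no | 48.7 | 45.6 | 25.7 | 45.6 | 48.7 |
| 8% | 0 | yes | 48.7 | 38.8 | 48.7 | 59.4 | 48.6 |
| 8% | 70% | yes | 48.7 | 35.2 | 25.9 | 55.8 | 48.8 |
| 3% | 70% | no | 21.6 | 19.9 | 9.4 | 19.9 | 21.6 |
| 3% | 70% | yes | 21.6 | 14.9 | 9.3 | 26.5 | 21.5 |

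The second row can be checked by hand.
- A = (0.4868 − 0.056)/0.944 = 45.6%.
- For B, failures still rated are 0.3 × (1 − 0.92⁷) + 0.08 × 0.92⁷ = 0.1326 + 0.0446 = 0.1773. Non-failures are 0.92⁸ = 0.5132. B = 0.1773/(0.1773 + 0.5132) = 25.7%.

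**Open-label quadrants.** If a share w of a pooled denominator stays fixed at its Day 360 value, Day 720 reads (1 − w) × 48.68% + w × 28.36%. That is 42.6% for w = 0.3 and 38.5% for w = 0.5, against 48.7%.

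**What this shows.** Without re-treatment or loss, crude percentages are unbiased. With either, the same data give values below, at or above the truth, depending on the denominator. Kaplan-Meier in all responders, with re-treated quadrants counted as events, stays within 0.1 point of the truth in these scenarios.

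**The case against.** A reader might infer that the analysis systematically removes recurrences from its own denominator and so understates recurrence at all four time points. The documents do not support that.

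- Section 17.2 dates the end of durability at the single return-to-baseline visit when re-treatment cuts off later ones. Re-treated quadrants are therefore meant to count as failures.
- Section 11.3.2 governs who attends visits beyond Day 360. It is not written as an exclusion from the analysis population.
- Recurrences that are not re-treated and stay under follow-up remain in the denominator.
- A re-treated subject continues with visits and will normally have ratings after Day 180. Section 17.2.4 does not require those ratings to precede re-treatment. Re-treatment before Day 180 also needs the blind to be broken and one observation visit completed (section 12.1.3), and the unblinding date is not given.
- Pooling of open-label quadrants at 540 and 720 days is not stated, and separate subsets are defined.
- The study is an uncontrolled, descriptive extension whose primary objective is safety.

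All of this stands, and it rules out a claim of fixed direction or known size. It does not supply what is missing. Section 17.5.2 does not refer to the 17.2 rule or say that earlier failures carry forward to 540 and 720 days. The 17.2 rule cannot restore a responder who recurred and left before Day 180. The all-treated statement in 17.2 also does not match the populations in 17.2.4.

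Part of 17.2 is redacted, and the combined document contains protocol text without a separate SAP. If a SAP defines denominators and censoring, the point narrows to aligning the texts.

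**Conclusion.** The point holds as a gap in specification with a better method at hand. For a quantity that section 17.2 defines as a time, section 17.5.2 plans crude percentages in a population conditioned on later follow-up, with no visible per-period denominator or censoring rule.

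Bias is downward if failures drop out or if unobserved time counts as success. It is upward if failures are carried forward while non-failures who left are dropped. It is nil without re-treatment or loss.

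The size cannot be determined from the documents. The 25.9% to 55.8% range around a true 48.7% is illustrative. It rests on assumed rates, loss unrelated to recurrence, and early re-treated quadrants falling outside the population. Because durability is secondary and descriptive here, this is a worthwhile low-cost improvement and not a flaw that undermines the study.

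**What to change.** Change the analysis text in sections 17.2.4 and 17.5.2:

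1. Remove the condition requiring ratings at Day 180 or later, and align the population with section 17.2.
2. Estimate cumulative recurrence in all active responders by Kaplan-Meier or an interval-censored method. Use every scheduled rating, timed by actual days since first injection, so that an early-termination rating does not stand in for Day 360 or Day 720.
3. Count return to baseline as the event. Include re-treated quadrants, dated no later than re-treatment and consistently with section 17.2.
4. Censor at the last rating, and at Day 360 at the latest for open-label quadrants.
5. Report double-blind and open-label quadrants separately, with 540- and 720-day estimates for EN3835-201 quadrants only. Give 95% confidence intervals and numbers at risk.

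No visit, eligibility or treatment rule changes, and the ratings needed are already scheduled. The cost is slightly more analysis work, and reported durability may look less favourable. Censoring at the last rating still assumes that loss is unrelated to recurrence, so reasons for leaving should be shown beside the estimates.
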